10.0 STUDY PROCEDURE

The procedure will be performed in accordance with the Instructions for Use (IFU) provided with the study device (**Appendix A**). A commercially available 6mm diameter synthetic graft will be used. Such grafts may include conventional ePTFE grafts or grafts designed for early cannulation (within 24-48 hours). The study procedure will be performed in an operating room that has fluoroscopic imaging capability for guiding placement of the VIG. The anesthesia regimen will be determined at the physician's discretion; there are no study-specific anesthesia requirements. A regional nerve block is typically performed for placement of an AVG. Standard, routine hemodynamic monitoring will be performed to assess cardiovascular status throughout the procedure. Heparin anticoagulation may be provided at the physician's discretion.

Small skin incisions will be made for tunneling the graft under the skin in a standard manner. The VIG device is provided pre-loaded within a customized catheter-based delivery system for over-the-wire delivery. The VIG is inserted through an introducer sheath placed in the target vein so that the 'vessel end' of the VIG is deployed within the vein, and the 'graft end' extends out of the vein for connection to the graft. Delivery and deployment will be performed under fluoroscopic guidance. The VIG will be deployed first, connected to the AVG, then the graft and VIG will be flushed and clamped. The arterial anastomosis will then be created using a standard suturing method.

NOTE: Although not expected, in the event that connection of the venous graft segment using the VIG is attempted but not able to be completed, the venous anastomosis should be completed using standard suturing. Such situations will be considered as a procedure failure.

Following establishment of the AV circuit, the skin incisions will be sutured closed using standard techniques. The subject will be moved to a recovery area for monitoring prior to discharge. It is anticipated that most subjects will be discharged the same day or within 24 hours following the AVG implant procedure.

Use of Clamps

To avoid mechanical damage or disruption to the AVG or VIG, surgical clamps or other tools with teeth or other sharp features should not be used during the AVG implant procedure. An atraumatic or guarded (e.g., rubber) clamp should be used for clamping the AVG, as needed. Do not clamp or manipulate the VIG with surgical tools. Use only gentle pinching with the fingers to hold the VIG and to control hemostasis.

Other Treatment Immediately after Deployment of the VIG

It is anticipated that no other interventional treatments will be required during the implant procedure. At the venous anastomotic site, no further treatment should be provided if the luminal diameter is \geq 90% of the adjacent normal vessel, based on operator's assessment. If the luminal diameter is $<90\%$, balloon angioplasty may be performed as follows:

After deployment, the nitinol-reinforced VIG *may* be smoothed and more fully seated against the vessel wall by inflating an angioplasty balloon. Balloon treatment should be performed according to the manufacturer's instructions, by a physician skilled in peripheral vascular interventional techniques. The balloon diameter used should be equal to that of the VIG diameter and should be no larger than 6mm when used to treat the VIG segment that is within the AVG. The balloon should be inflated within the VIG along the entire length. Multiple

inflations may be needed. To avoid possible displacement of the VIG, the physician should assure that the balloon is fully deflated prior to carefully removing the balloon.

Vascular Graft for Hemodialysis

Vascular grafts that meet the following requirements, as determined by the physician, may be used: commercially available, straight (not-tapered), 6 mm inner diameter ePTFE grafts. Adequate graft length and trimming must be carefully determined to facilitate optimal positioning after the venous and arterial graft anastomoses have been completed. The graft should never be too short.

Treatment of Ipsilateral Central Venous Stenosis Prior to Enrollment

Ipsilateral central venous stenosis is a study exclusion. However, a patient with central venous stenosis may be considered for the study following successful treatment of the stenosis. Central stenosis angioplasty may be performed first, then immediately followed with the study procedure. The patient may be enrolled if, as assessed by the investigator, the central stenosis has <30% residual stenosis, which is the KDOQI threshold for successful intervention. The patient should not be enrolled if the residual stenosis is >= 30% or if the investigator determines that the treatment could impact the ability to assess the study endpoints (e.g., acute device success, graft patency, safety).

Study Device Failure, Defect, or Suspected Device Problem

Device malfunction is defined as *any occurrence in which the study device does not perform as intended, when used or attempted to be used in a study procedure*. As described in the device Instructions for Use (IFU), a visual examination of the VIG should be performed at the time of opening the packaging and prior to use in a subject. Defective devices (obvious or suspected) should not be used. A replacement VIG should be obtained and the study procedure continued. A device accountability log will be used to account for all used and opened/unused devices in this study.

If a VIG defect or malfunction is discovered/suspected any time prior to vascular deployment, the VIG should not be used. A replacement device/component should be used and the study procedure continued. A Device Malfunction form must be completed for all device malfunctions, failures or suspected failures, and the defective product identification should be recorded on the device accountability log. Whenever possible, a defective/suspected defected VIG should be returned to the Sponsor for evaluation.

The Device Malfunction form (eCRF) should be used to report and provide details of situations in which the VIG does not perform as intended. Failure of the VIG to perform as intended may be potentially be due to a variety of reasons, including defect or suspected defect in the device itself or the delivery system; operator error; anatomic issues; or other reasons. If use of the VIG is attempted but ultimately the device is not able to be used, a Device Malfunction eCRF should be submitted to report the surrounding details.

NOTE: Device Malfunctions should be reported on the Device Malfunction eCRF within 24 hours of discovery. 24-hour reporting of device malfunctions will assist with Sponsor's efforts to assess whether any SAEs associated with a device malfunction may also have occurred.

Bailout Procedure

Bailout procedures are not anticipated, but could potentially be required if, for example, the VIG does not deploy correctly, does not seal correctly, is not deployed at an acceptable location, or if there are any major vascular events. In such cases, the subject should be referred for surgical intervention. No attempt should be made to remove an improperly deployed VIG using percutaneous methods.

Assessment of Graft Flow at the End of the Study Procedure

An AVG placed using the VIG and a sutured arterial anastomosis typically has a pulse and/or thrill which is easily palpable over the skin or directly in the AVG prior to closure of the surgical incisions. Thus, the AVG flow assessment is similar that used for standard sutured AVGs. An optimal method to confirm AVG patency at the end of the implant procedure is to feel a thrill near the arterial anastomosis or confirm a Doppler signal. Auscultation using a sterile or covered stethoscope is also acceptable. At the physician's discretion and as warranted, a final angiogram may also be performed to verify patency of the graft.

Initial Use of the Study Graft for Hemodialysis

Initial hemodialysis cannulation of AVGs placed with the VIG should be performed in accordance with the graft manufacturer's Instructions for Use. After needle withdrawal, use gentle, non-occlusive digital pressure to compress the cannulation site until hemostasis is achieved. The VIG should NOT be directly cannulated. In accordance with standard practice, once placed, AVGs should be used for hemodialysis access as soon as deemed appropriate by the nephrologist and/or operator. For standard ePTFE AVGs, the time from placement to first cannulation is typically after two weeks. Early cannulation AVGs can be used within one week after placement. Every effort should be made to minimize infection risk by removing central catheters as soon as possible.

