5.0 STUDY OBJECTIVE

The objective of the current study is to demonstrate that the 6-month cumulative patency of AVGs connected with the InterGraft™ VIG connector is similar to that of AVGs connected using standard sutured anastomoses.

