8.0 STUDY ENDPOINTS

Primary Endpoint

The primary endpoint is cumulative patency at 6 months, defined as the percentage of subjects free from loss of access of the study graft for hemodialysis, assessed at 6 months.

Secondary Endpoints

Secondary endpoints for the study include:

1. Acute device success, defined as AV graft flow at the end of the procedure as determined by palpable graft thrill and/or audible bruit, without significant bleeding or emergent surgery.
Primary Unassisted Patency at 6 Months, defined as the percentage of subjects free from the first occurrence of either access thrombosis or an access procedure performed to maintain access patency.
2. Time to First Cannulation, defined as the time from initial access placement to the first graft cannulation.
3. Number and type of interventions required to maintain secondary patency
4. Number and type of serious adverse events (SAEs) through 6 months. SAEs include the following: death, emergent surgery, infection requiring treatment (e.g., prolonged or intravenous antibiotic therapy), significant bleeding (defined as bleeding requiring treatment), and pseudoaneurysm.

Expected interventions for restoration of patency will be documented and reported separately, are reflected in the evaluation of cumulative patency, and will not be tabulated again as SAEs.

Endpoints will be evaluated acutely (at the time of implant), at time of any AVG intervention, at two weeks, and monthly through 6 months for all subjects. The study AVG patency evaluation starts immediately after the index procedure is completed (e.g., subject leaves the surgery suite). This means that once the AVG is created, patency evaluation begins. The occurrence of acute thrombus and treatment thereof during the index procedure while the vascular access is being created does not trigger the loss of primary patency.

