2.2.2 Secondary Endpoints

Secondary endpoints for the study include:

1. Acute device success, defined as AV graft flow at the end of the procedure (determined by palpable graft thrill and audible bruit), without significant bleeding or emergent surgery
2. Primary Unassisted Patency at 6 Months, defined as the percentage of subjects free from the first occurrence of either access thrombosis or an access procedure performed to maintain access patency.
3. Time to First Cannulation, defined as the time from initial access placement to the first graft cannulation.
4. Number and type of interventions required to maintain secondary patency
5. Number and type of serious adverse events (SAEs) through 6 months. SAEs include the following: death, emergent surgery, infection requiring treatment (e.g., prolonged or intravenous antibiotic therapy), significant bleeding (defined as bleeding requiring treatment), and pseudoaneurysm.

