4.2 Analysis Populations

All subjects who meet the enrollment criteria and in whom the VIG InterGraft™ Connector is attempted will be included in the ITT primary analysis population. Roll-in cases will not be included in the main study analyses.

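### Acute device success can count a conversion to a sutured venous anastomosis as a success, and the protocol and SAP apply different thrill/bruit criteria

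*Protocol*

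**What the plan says.** **Conversion.** The note in Protocol 10.0 covers a VIG connection that is attempted and cannot be completed: "the venous anastomosis should be completed using standard suturing. Such situations will be considered as a procedure failure".

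**Endpoint, protocol.** Protocol 8.0 defines acute device success as AV graft flow at the end of the procedure, "determined by palpable graft thrill and/or audible bruit, without significant bleeding or emergent surgery".

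**Endpoint, SAP.** SAP 2.2.2 defines it as "AV graft flow at the end of the procedure (determined by palpable graft thrill and audible bruit), without significant bleeding or emergent surgery".

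**Population and analysis.** SAP 4.2 keeps every eligible subject "in whom the VIG InterGraft™ Connector is attempted will be included in the ITT primary analysis population", and Protocol 18.0 likewise includes subjects on the basis of attempted use. SAP 4.4 summarises acute device success by a rate and a 95% confidence interval. It attaches no hypothesis or significance level and states that such intervals are not for labeling.

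**Relation of the documents.** SAP 1.0 presents the SAP's procedures as consistent with the Investigational Plan, with further detail on implementation.

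**The concern.** Acute device success is the only listed endpoint aimed at how the device performs at implant. A reader will take the rate as the share of attempts in which the connector did its job. As written, the definition asks whether the graft flows, not whether the VIG made the venous connection. The one rule that does call a conversion a failure, in Protocol 10.0, is never linked to the endpoint.

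The flow wording adds a second ambiguity, which does not depend on any conversion occurring. The rate can change with the document the analyst follows, and neither document says which prevails. What is at stake is the accuracy of one reported rate and its interval, in a study intended to support a 510(k) submission.

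**Working it through.** **Step 1: score the same subject under each rule.** Assume no significant bleeding and no emergent surgery in every row.

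| Venous connection | Signs recorded | Protocol 10.0 note | Protocol 8.0 | SAP 2.2.2 |
|---|---|---|---|---|
| VIG | thrill and bruit | not a failure | success | success |
| VIG | one sign only | not a failure | success | not a success |
| Converted to suture | thrill and bruit | procedure failure | success | success |
| Converted to suture | one sign only | procedure failure | success | not a success |

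Row 3 is the first problem: both documents score a success for a case that Protocol 10.0 calls a failure. Rows 2 and 4 are the second: the documents disagree with each other. Because the population is defined by attempted use, converted subjects remain in the denominator.

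**Step 2: effect of one subject.** The documents state no figure for acute device success, so there is none to reproduce. Taking the planned sizes from Protocol 18.0 as denominators:

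- N = 146 (evaluable): 1/146 = 0.68 percentage points per subject.
- N = 158 (with the allowance for loss to follow-up): 1/158 = 0.63 percentage points per subject.

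The same step applies to each conversion and, separately, to each subject with only one sign recorded.

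**Step 3: illustration.** The documents give no conversion count for this study. Let k be the number of affected subjects in 146 and assume that all others succeed. The rate is (146 − k)/146. The exact (Clopper-Pearson) limits for x successes are the 0.025 quantile of Beta(x, n − x + 1) and the 0.975 quantile of Beta(x + 1, n − x).

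| k (assumed) | Counted as success | Not counted as success (95% CI) |
|---|---|---|
| 0 | 100% (97.5 to 100) | 100% (97.5 to 100) |
| 1 | 100% (97.5 to 100) | 99.3% (96.2 to 100.0) |
| 3 | 100% (97.5 to 100) | 97.9% (94.1 to 99.6) |
| 5 | 100% (97.5 to 100) | 96.6% (92.2 to 98.9) |
| 8 | 100% (97.5 to 100) | 94.5% (89.5 to 97.6) |
| 15 | 100% (97.5 to 100) | 89.7% (83.6 to 94.1) |

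For the flow wording, read the middle column as the protocol's rate and the right-hand column as the SAP's, with k the number of subjects with one sign only.

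**Step 4: does anything else move?** The sample size in Protocol 18.0 and SAP 2.3 rests on 6-month patency: 84.6% against a goal of 75%, one-sided alpha 0.025. An exact binomial check at N = 146 rejects at 120 or more patent grafts, with alpha 0.0249 and power 82.3%. Acute device success enters none of these inputs.

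**The case against.** **The note already calls a conversion a failure.** Someone reading the protocol as a whole could score it so. That is fair, and it is why the claim is that a conversion *can* count as a success, not that it *will*. But the note speaks of a procedure failure, the endpoint of device success, and no text joins them.

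**Conversions should be few, and they are recorded.** Protocol 10.0 does not anticipate them, calls for a replacement VIG when a fault is found before vascular deployment, and asks for a Device Malfunction eCRF when an attempted VIG cannot be used. The first-in-human series reports deployment success in 9 of 9 subjects. This limits the likely size of the effect. It does not link the malfunction form to the endpoint, and no conversion count is promised.

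**Both signs will probably be checked.** Table 1 in each document names thrill and bruit at the end of the procedure, although the protocol gives them as examples. This may keep one-sign records rare; it does not reconcile the definitions. Nor is the SAP wording mere added detail, since it changes who succeeds.

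**Undefined terms.** A reader might infer a further defect because emergent surgery is undefined while a bailout case is handled by "In such cases, the subject should be referred for surgical intervention", and because emergent surgery also appears in the list beginning "SAEs include the following: death, emergent surgery, infection requiring treatment". A reader might likewise note that one optimal flow check "is to feel a thrill near the arterial anastomosis or confirm a Doppler signal" includes a method in neither definition. These are missing details. Some bailouts may fail the endpoint as emergent surgery, which narrows the first problem, and the flow-check text guides the operator without setting a scoring rule.

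**Conclusion.** Both points hold on the text. A non-emergent sutured conversion with adequate flow can be reported as an acute device success, and a subject with one flow sign is scored differently by the two documents. The size is about 0.7 percentage points per affected subject at N = 146. It is zero for the first point if no conversions occur, and zero for the second if no otherwise successful subject has only one sign recorded. Every count in the illustration is an assumption.

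A reader might infer that the primary result is also at risk, because the objective concerns whether "the 6-month cumulative patency of AVGs connected with the InterGraft™ VIG connector is similar to that of AVGs connected using standard sutured anastomoses" while converted grafts stay in the analysis. The documents do not support that. Analysing observed graft status in everyone with an attempted VIG is a legitimate intention-to-treat choice, stated in both documents. Conversions should not be rescored as patency failures, and the absence of a planned estimate among VIG-completed grafts is not an error. The harm is confined to one descriptive rate and its interval.

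**What to change.** 1. In Protocol 8.0 and SAP 2.2.2, add that acute device success requires the venous anastomosis to have been completed with the VIG. State that a conversion under the Protocol 10.0 note is scored as not successful.
2. Put one identical thrill/bruit criterion in both documents. The passages must be reconciled; the choice is the sponsor's and should be made before acute results are summarised.
3. Report the number of conversions beside the acute success rate.

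**Cost.** Wording in two documents and one extra count. The reported rate may be slightly less favourable. The case report form (Appendix C) is not in the material at hand, so the sponsor should confirm that it records how the venous anastomosis was completed and records the two signs separately.

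**Leave unchanged.** The intention-to-treat primary analysis, the primary test and the sample size.

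**Optional.** Define emergent surgery for scoring, say how a Doppler-only check is scored, and add a descriptive Kaplan-Meier estimate among VIG-completed grafts. That subset is selected after the attempt, so it could support the primary result but not replace it.

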11.0 FOLLOW-UP PROCEDURES AND GRAFT INTERVENTIONS

Subject Management

Prior to discharge, the study investigator or their designee should insure that the subject understands the postoperative care requirements, as determined by the physician, and the required follow-up schedule. The two-week visit should be scheduled.

It is recommended that investigators follow the *Fistula First Guidelines* for vascular access monitoring (http://esrdnetwork18.org/pdfs/QI%20-%20FF%20Tools/FFTTool_VAMPFlowChrt.pdf or current).

Pharmacologic Regimen

There are no study-specific pharmacologic requirements. The need for intraoperative and postoperative anticoagulation therapy should be based on subject history and maintained as deemed appropriate by the physician. Anticoagulation/anti-platelet therapy will be recorded on the case report form (CRF).

Follow-up Evaluations

Subjects will be followed at two weeks and monthly thereafter through six months to assess AVG patency and complications. Measurement of access flow rate is part of standard care. Data from routine AV access flow monitoring performed as part of usual care, as available, will also be collected.

Graft ultrasound evaluation should be performed at the 3 month and 6 month follow-up visits and the results recorded on the CRF.

NOTE: For reference and in accordance with standard care, baseline flow measurements are typically assessed during 2 dialysis sessions 2 weeks apart; and monthly measurements will be performed thereafter. An access flow rate < 500 mL/min or a drop in access flow rate of 25% from baseline should trigger an angiographic evaluation of the AVG and possible intervention.

Telephone follow-up for subjects that miss the final (6 month) follow-up visit

If a study subject misses or is unavailable/unwilling to return for the final 6 month follow-up visit, telephone follow-up with the subject or their dialysis center should be attempted to determine the patency status of the AVG at 6 months (the primary study endpoint), and to gather as much additional information as possible in order to complete the 6 month follow up and study completion eCRFs. Telephone follow-up with subjects should be done only if the subject is unwilling or unable to come in. If the subject cannot be reached, then the dialysis center should be contacted (if allowed) in order to determine AVG patency at 6 months. If it is not possible to reach the subject by phone or to contact the dialysis center, then the subject will be considered as lost-to-follow up.

Post-procedure Graft Interventions

As per standard care following the AVG implant procedure, AVG interventions should be avoided within the first 7 days following the index AVG implant procedure. As warranted and determined by the physician, standard balloon angioplasty and thrombectomy procedures may be performed within the AVG, VIG, and adjacent native artery and vein. Mechanical thrombectomy devices that use spinning, rotating or other movable parts should NOT be used in the study, as this may result in entanglement or other damage to the VIG. The balloon diameter used should be equal to that of the VIG diameter and should be no larger than 6mm when used to treat the VIG segment that is within the AVG.

Summary of Tests and Procedures

The required schedule for subject treatment and follow-up evaluation is shown in **Table 1**.

Table 1: Schedule of Subject Treatment and Evaluation

Timeframe (window)	Test/Procedure
Pre-procedure (within 30 days)	Baseline imaging of target AVG site (performed as part of standard care) Baseline labs: Hgb, Hct, WBC, platelets
Pre-procedure (within 24 hours)	Urine pregnancy test for female subjects with reproductive potential
Immediately following end of AVG implant procedure (before leaving surgery suite)	Confirmation of AVG flow (e.g., palpable thrill, audible bruit). At the physician's discretion and if warranted, an angiogram may also be performed to confirm patency.
Post- procedure (within 48 hours)	Post procedure labs: Hgb, Hct
At discharge	Confirmation of AVG flow (palpable thrill, audible bruit)
2 weeks following the procedure (14 +4/-7 days)	Clinical follow- up with AVG evaluation (includes collection of information regarding any subsequent hospitalization, AEs, AVG interventions)
30, 60, 90, 120, 150,180 days following the procedure (± 14 days)	Clinical follow- up with AVG evaluation (includes collection of information regarding any subsequent hospitalization, AEs,

	AVG interventions) AVG flow rate evaluation (ultrasound or similar) is performed at the 90-day and 180-day follow-up visits.
--	---

Final Events

The following final events will justify cessation of study follow-up: death, AVG abandonment, lost to follow up (at least 3 attempts to contact the subject should be made and documented), or completion of study follow-up.

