6.0 STUDY DESIGN

This is a multicenter, prospective, non-randomized design study. All enrolled subjects will receive the VIG device and will have a standard sutured arterial anastomosis. The study allows for a maximum enrollment of 173 subjects, including a provision for 12 subjects lost to follow-up and up to 15 roll-in cases. Data from roll-in subjects will not be included in the primary analysis but will be analyzed separately.

The study includes up to 23 participating clinical centers. Study site investigators will be physicians skilled in AVG placement and interventional techniques. Study data will be collected up to the point at which each subject has completed the 6-month endpoint or experienced a terminal study endpoint.

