The occurrence of AEs, including SAEs and UAEs, will be monitored throughout the study duration. Adverse event information will be collected and reported on designated AE forms, assessed and classified by the principal investigator as serious/not serious. The investigator will also determine the relatedness of the AE to the study device and study procedure according to the following definitions:

- Related (AE is clearly related to the device/procedure);
- Possibly related (AE may be related to the device/procedure);
- Unrelated (AE is clearly not related to the device/procedure).

Procedure-related AEs are AEs that occur during the time interval from when the subject enters and leaves the surgical treatment suite for the index procedure (e.g., AVG implant procedure). Thus, the procedure includes use of the study device, as well as any treatments or procedures that are applied before or after the study device (eg, anesthesia, suturing of incision sites after AVG is completed), while the subject is in the surgical suite.

Device-related AEs are AEs related or possibly related to the study device or to the study device procedure which includes delivery, deployment, and attachment of the study device to the AVG.

Device-related events that occur during the study procedure are also procedure-related events.

Procedure-related events may not necessarily be related to the study device; for example, a procedure event such as an anesthesia reaction would not be related to the study device.

Device-related events may also occur after the study procedure, for example, fracture of metal strut in the VIG.

For situations in which a study subject has a serious adverse event (SAE) that results in abandonment of the study AV access site, the subject should be followed to the next follow-up visit after the study AVG is abandoned. This is done in order to collect general information about the subject's health status after the AVG is abandoned.

After that visit, the subject can then be formally withdrawn from the study. This means that the date that AVG patency is lost and the date of study withdrawal are not necessarily the same date.

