4.4 Secondary Endpoints

The following secondary endpoints will be evaluated in the study, but there are no formal hypotheses that are tested or associated significance levels assigned to results. Nominal confidence intervals may be calculated in summarizing clinical results for secondary endpoints but not for purposes of product labeling.

1. Acute device success will be summarized by the success rate and associated 95% confidence interval.
2. Primary Unassisted Patency at 6 Months will be summarized by the patency rate and associated 95% confidence interval.
3. Time-to-First-Cannulation will be summarized by the median time and frequency distribution.
4. Number and type of interventions required to maintain secondary patency will be summarized by the frequency distributions of numbers and types of interventions.
5. Number and type of serious adverse events (SAEs) will be summarized by frequency distributions of the numbers and types of SAEs, the subject rates of SAEs by type, and the proportion of subjects with at least one SAE.

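### The SAE endpoint is labelled through 6 months, but safety follow-up may end at graft abandonment and the crude SAE summaries make no allowance for it

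*Protocol*

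**What the plan says.** Two sets of provisions bear on how long SAEs are collected.

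**Six months for everyone.** Protocol 8.0 lists as a secondary endpoint "Number and type of serious adverse events (SAEs) through 6 months". The same section has endpoints evaluated at implant, at any graft intervention, "at two weeks, and monthly through 6 months for all subjects". Protocol 11.0 (Follow-up Evaluations) also has subjects seen through six months for patency and complications.

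**Stopping earlier.** Protocol 11.0 (Final Events) says: "The following final events will justify cessation of study follow-up: death, AVG abandonment, lost to follow up". SAP 3.2 repeats this. Protocol 6.0 adds: "Study data will be collected up to the point at which each subject has completed the 6-month endpoint or experienced a terminal study endpoint"; SAP 2.0 says the same. Protocol 21.0 makes one exception. When an SAE results in abandonment, "the subject should be followed to the next follow-up visit after the study AVG is abandoned". Then: "After that visit, the subject can then be formally withdrawn from the study". No further safety follow-up is set out for a graft abandoned without an SAE.

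**Analysis.** Protocol 18.0 and SAP 4.4 summarize SAEs by frequency distributions, subject rates by type (not defined further) and "the proportion of subjects with at least one SAE". Neither mentions time at risk, a time-to-event method or a rule for incomplete follow-up. The censoring and missing-data rules in SAP 4.9 concern the primary endpoint only.

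**The concern.** An endpoint with a six-month window needs either six months of observation or a method that allows for less. Here observation may end when the graft is given up, so the subjects with the worst device outcome can have the shortest safety follow-up. The worse the device performs, the less of its safety record is observed.

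The missing time can contain relevant events. Protocol 3.0 describes the connector as a permanent implant. Protocol 21.0 accepts that device-related events can arise after the procedure and gives a strut fracture as an example. Of the SAEs listed in Protocol 8.0, death, infection and pseudoaneurysm do not need a patent graft. Protocol 2.0 associates catheter dialysis with more infection, thrombosis, morbidity and mortality. The documents do not say how subjects dialyze after abandonment. If some return to a catheter, their SAE rate may rise in the very period that is not observed; that is an inference, not a figure in the plan.

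Safety carries no hypothesis test, so these descriptive summaries are the safety evidence that will go into the 510(k) submission mentioned in Protocol 2.0.

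**Working it through.** **Inputs from the documents.** Expected 6-month patency 84.6%, performance goal 75%, 146 evaluable subjects, 8% loss to follow-up, 158 enrolled (Protocol 18.0, SAP 2.3). Visits at 2 weeks and then at 30-day intervals to day 180 (Protocol 11.0, Table 1). The design figures reproduce: with n = 146 and success at 120 or more patent grafts, the exact binomial test has alpha 0.0249 and power 82.3%, and 146 × 1.08 = 157.7, or 158.

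**Assumptions.** The documents give no SAE rate, no timing of graft loss and no SAE hazard after abandonment. I take a constant loss rate, vary the timing, and use true SAE risks of 10 to 40%.

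**1. Subjects affected.** 158 × 0.154 = 24.3, about 24.

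**2. Unobserved time if follow-up stops at abandonment.** Over 6 months the cumulative hazard of loss is H = −ln(0.846) = 0.1672.
- Mean observed fraction of the window = 0.154 / 0.1672 = 0.921, so 7.9% of subject-time is lost.
- All of it falls on failed grafts: 0.079 / 0.154 = 51% of their window. Their mean time to loss is about 2.9 months.
- If every failed-graft subject had the extra visit of Protocol 21.0, the losses would be 44% of their window and 6.7% overall.
- Timing: if all losses came at month 1, 0.154 × 5/6 = 12.8% overall; if all came at month 5, 0.154 × 1/6 = 2.6%.
- At the 75% performance goal: 1 − 0.25 / 0.2877 = 13.1%.
- Adding 8% loss to follow-up at 84.6% patency: 0.846 × 0.92 = 0.7783, −ln(0.7783) = 0.2506, and 1 − 0.2217 / 0.2506 = 11.5%.

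**3. Effect on the proportion with at least one SAE.** Let q be the true 6-month risk and M = −ln(1 − q). With the same hazard before and after abandonment and no extra visit, the observed proportion is

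M / (M + H) × [1 − (1 − q) × 0.846].

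For q = 20%: M = 0.2231, so 0.2231 / 0.3904 × (1 − 0.6768) = 0.1847. Among failed grafts alone: (0.1847 − 0.846 × 0.20) / 0.154 = 10.1%, against a true 20%.

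If the hazard doubles after abandonment, the crude figure is unchanged but the true risk becomes

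0.846q + 0.154 − H·e^(−2M) × [1 − e^(−(H − M))] / (H − M).

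| Risk q at the pre-abandonment hazard | Crude figure | Shortfall, same hazard | True risk, hazard doubled | Shortfall, hazard doubled |
|---|---|---|---|---|
| 10% | 9.2% | 0.8 points | 10.7% | 1.5 points |
| 20% | 18.5% | 1.5 points | 21.3% | 2.8 points |
| 30% | 27.8% | 2.2 points | 31.8% | 4.0 points |
| 40% | 37.1% | 2.9 points | 42.1% | 5.0 points |

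With the extra visit for every failed graft and the same hazard, the 20% case gives 18.7% and the 30% case 28.1%.

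**The case against.** **Stopping is permitted, not required.** Final events justify ending follow-up; they do not order it. A reader might infer that follow-up always stops at abandonment. The documents do not support that: Protocol 8.0 promises six months for all subjects, and Protocol 21.0 requires one more visit after some abandonments. What stands against the plan is that its sections disagree and that sites may follow the shorter rule.

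**The denominator is not stated.** SAP 4.4 does not say that SAE proportions are taken over all subjects. That is the natural reading, but it remains a reading.

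**The effect is modest.** With an unchanged hazard the shortfall stays below one standard error: at 30% and n = 146 that is √(0.3 × 0.7 / 146) = 3.8 points. SAEs have no formal hypothesis, and events before exit are reported within 24 hours and reviewed. All this is fair, but a shortfall always in one direction and concentrated in failed grafts is not sampling noise.

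**A statistical adjustment alone would not repair it.** Kaplan-Meier censored at abandonment assumes that abandonment says nothing about later SAE risk. In the 20% row with a doubled hazard it would return about 20% against a true 21.3%. This objection stands and shapes the fix. It also stands that later SAEs may belong to a replacement access.

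**Interventions.** A reader might infer that the planned "frequency distributions of numbers and types of interventions" are understated in the same way. They are not. The endpoint covers only interventions to maintain secondary patency, and none can occur once the graft is abandoned, so abandonment removes nothing from the count. A graft lost in month 1 without intervention does look like one that needed none, but its loss is an event in the primary analysis.

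**Conclusion.** The concern holds for SAEs. The protocol sections on SAE follow-up cannot all describe the same endpoint, and the planned summaries do not allow for the difference. As written, the SAE proportion is not a 6-month figure and is likely understated, mainly in subjects whose grafts failed.

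The loss of observation rests on the plan's own 84.6% patency and an assumed constant loss rate. The 7 to 8% of total subject-time becomes about 3 to 13% as the assumed timing of losses varies. The shortfall in the SAE proportion rests further on assumed SAE risks and hazards, so it is an illustration and not a prediction. It is modest overall and large within the failed-graft group.

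The primary Kaplan-Meier analysis counts abandonment as an event and is unaffected. Intervention counts are not biased by abandonment. The change is worth making because it is cheap and because these summaries are the trial's safety evidence.

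**What to change.** 1. **Protocol 6.0, 8.0, 11.0 and 21.0; SAP 2.0 and 3.2.** Reconcile these sections so that abandonment ends patency follow-up only. Collect SAEs and vital status to day 180 in every subject who has not died, withdrawn consent or been lost. Where a visit is not possible, use the telephone or dialysis-center contact that Protocol 11.0 already provides for a missed final visit.
2. **SAP 4.4 and 4.5.** Report the 180-day SAE proportion from that fuller follow-up and state its denominator. For follow-up that is still incomplete, add time to first SAE (deaths counted as SAEs) and SAEs per subject-month. Do not use Kaplan-Meier censored at abandonment in place of the added collection.
3. **Presentation.** Show SAEs before and after abandonment separately, because later events may reflect a replacement access.
4. **Optional.** Give interventions per patent-graft-month beside the planned counts.

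The cost is brief contacts for about 15% of subjects (about 24), some wording in both documents and a few table columns. Subjects already withdrawn after abandonment may not be recoverable; their number should be reported.
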